Page 52 12.1.3. Sample Size Calculation and Methods	Assuming a one-sided alpha level of 0.025 and a true event rate of 6.8%, an effective sample size of 1360 subjects will yield a greater than 98% power to reject the null hypothesis.	Assuming a one-sided alpha level of 0.025 and a true event rate of 6.8%, an effective sample size of 1360 subjects will yield a greater than 97% power to reject the null hypothesis.	Modification	Updated the power as consistent with Statistical Analysis Plan
Page 53 12.4. Analysis of the Primary Endpoint	The CD/MI rate at one year in a one-month clear population [timeframe: one month to one year] will be compared with the performance goal of 9.9% , with a one-sided Fisher's exact test at the 0.025 significance level.	The CD/MI rate at one year in a one-month clear population [timeframe: one month to one year] will be compared with the performance goal of 9.7% , with a one-sided binomial exact test at the 0.025 significance level.	Modification	Updated performance goal and test name as consistent with Statistical Analysis Plan
Page 53 12.5. Analysis of Secondary Endpoints	For secondary endpoints, event/success rates, and 95% confidence interval will be provided.	For secondary endpoints, event/success rates, and 95% two-sided confidence interval will be provided.	Addition	Clarification on the confidence interval
Page 53 12.7. Analysis of Subgroups	Subgroup analyses of the primary endpoint include the following patient characteristics.	Subgroup analyses of the primary endpoint include but are not limited to the following patient characteristics.	Addition	Clarification on the subgroup analyses as consistent with Statistical Analysis Plan

Medtronic Controlled Information

27 January 2020

Page 4 of 16

Revision 4.0

1. Version History

Version	Summary of Changes	Author(s)/Title
1.0	Initial release	[name] Principal Statistician
2.0	
1. Section 3.1 removed definition of one-month clear because it is also defined in section 6.12. Section 6.1 additional details for the one-month clear definition, clarifications for as treated one-month clear definition as primary analysis population. Added intent-to-treat (ITT) set for one-month clear and definition of pivotal date3. Section 6.2 added ITT set and moved the comparison between Onyx arm and BioFreedom to section 6.8 where all comparisons between Onyx arm and BioFreedom are in the same section.4. Section 6.4.4 removed secondary analysis and analysis on the Per Protocol (PP) set as critical analyses are already covered by multiple populations: intent-to-treat, as treated, one month clear, and as treated one month clear.5. Section 6.4.5 clarification of section by removing “although only cardiac death and myocardial infarction occurring on or before one year will count toward the primary endpoint”6. Section 6.5.1 to be consistent with Section 6.1, replaced PP set with ITT and removed the sentences “the acute success will be analyzed on the AT set, the AT one-month clear population, and PP set.” and “For publication purpose, the secondary endpoints analysis may also be performed based on ITT set”7. Section 6.6 added landmark analysis8. Section 6.7 added subgroups and subgroup analyses of secondary endpoint, AT set. Removed SAPT compliance at 2 months, SAPT compliance at 6 months, and SAPT compliance at 12 months9. Section 6.8 added analysis for extension of Onyx One Global RCT study to include baseline demographic and clinical data and cumulative analysis and landmark analysis that will compare Onyx arm to BioFreedom arm10. Section 6.11 removed the third paragraph	[name] Principal Statistician
3.0	
1. Section 6.1 removed the sentence “Pivotal date is defined to be the date that a subject transitions from DAPT to SAPT.”2. Section 6.7 Changed subgroup “SAPT type after pivotal date” to “SAPT type after one month”3. Section 6.8 replaced “pivotal date” with “one month”	[name] Principal Statistician

Medtronic Controlled Information

056-F286, Statistical Analysis Plan Template Version A

This document is electronically controlled. Printed copies are considered uncontrolled.

Confidential

Onyx ONE Clear Study Statistical Analysis Plan

27 January 2020

Page 5 of 16

Revision 4.0

Version	Summary of Changes	Author(s)/Title
4.0	
1. Section 2 added the words “and publications” to the first sentence.2. Section 3.2 changed the word “all” to “appropriate” in the first sentence. Spelled out the word “definite” and “probable”.3. Section 6.1 capitalized the word “treated”4. Section 6.5 clarified the time points for secondary endpoint assessment. All secondary endpoints except acute success will be assessed at 1, 2 and 6 months, 1 year, and 2 years for AT set; also at 6 months, 1 year and 2 years for AT one-month clear set.5. Section 6.5.1 removed AT one-month clear set from the secondary analysis for the secondary endpoints because it is the analysis cohort for the primary analysis for the secondary endpoints. Removed ITT set from the secondary analysis because it is not needed for the clinical study report.6. Section 6.6 changed “vs” to “vs.”7. Section 6.6 was removed and the content was moved to section 6.7 because the landmark analysis is for publication only.8. Section 6.6 updated the definition of analysis cohort for this subgroup to “This only applies to one-month clear population and who actually transitioned to SAPT from DAPT.” for clarification purpose.9. Section 6.6 updated the wording for subgroup analysis on US vs. Japan to “US vs. Japan (p-value from comparing US subjects to Japan subjects will be calculated)”10. Section 6.7 added a sentence “This section describes the planned analyses for publication purposes only” to clarify the intention of the outlined analyses in this section.11. Section 6.7 added landmark analyses for publications.	[name] Principal Statistician

2. Introduction

This Statistical Analysis Plan has been designed to document, before data are analyzed, the rationale for the study design and the planned analyses that will be included in study reports and publications. This statistical analysis plan is developed based on the Onyx ONE Clear Study Clinical Investigational Plan (CIP).

The purpose of this study is to evaluate the clinical safety and effectiveness of the Resolute Onyx stent in subjects deemed at high risk for bleeding and/or medically unsuitable for more than one-month dual antiplatelet therapy (DAPT) treatment receiving reduced duration (one month) of DAPT following stent implantation. The primary endpoint is the composite rate of cardiac death and myocardial infarction at one year for a one-month clear population [timeframe: one month to one year].

The Onyx ONE Clear Study is a prospective, multi-center, single arm study for a commercially approved product. A total of 700 subjects will be enrolled in the United States and 100 subjects may additionally be enrolled in Japan. Subjects will be enrolled in up to 70 centers over an approximate 10-month period or until study enrollment is completed.

Medtronic Controlled Information

056-F286, Statistical Analysis Plan Template Version A

This document is electronically controlled. Printed copies are considered uncontrolled.

Confidential

Revision 4.0

A study report will be prepared for submission to FDA at the time when 700 US subjects have completed their 1-year follow up, for the purpose of seeking market approval. After all enrolled subjects have completed all protocol-specified follow-up, a final clinical report will be prepared and submitted.

Any deviations from the Statistical Analysis Plan will be described and justified in the Final Report, as appropriate.

3. Study Objectives

The primary objective of the study is to evaluate the clinical safety of the Resolute Onyx stent as compared to the Performance Goal (PG), with use of one-month DAPT in subjects deemed at high risk for bleeding and/or medically unsuitable for more than one-month DAPT treatment.

The secondary objective of the study is to evaluate the clinical effectiveness of the Resolute Onyx stent, with use of one-month DAPT in subjects deemed at high risk for bleeding and/or medically unsuitable for more than one-month DAPT treatment.

The following endpoints will be used to evaluate the study objectives.

3.1. Primary Endpoint

The primary endpoint is a composite rate of cardiac death and myocardial infarction at one year for a one-month clear population [timeframe: one month to one year]. The definition for one-month clear population is defined in section 6.1.

3.2. Secondary Endpoints

The following secondary endpoints will be assessed at appropriate follow-up time points (1, 2, 6 months, 1 and 2 years) except acute success:

1. Acute success (device, lesion, procedure)
 - Device success is defined as the attainment of <30% residual stenosis by QCA (or <20% by visual assessment) and TIMI flow 3 after the procedure, using the assigned device only.
 - Lesion success is defined as the attainment of <30% residual stenosis by QCA (or < 20% by visual assessment) and TIMI flow 3 after the procedure, using any percutaneous method.
 - Procedure success is defined as attainment of <30% residual stenosis by QCA (or <20% by visual assessment) and TIMI flow 3 after the procedure, using any percutaneous method without the occurrence of MACE during the hospital stay.
2. All deaths including cardiac death
3. Major adverse cardiac event (MACE)
 - Defined as death, myocardial infarction, or clinically driven repeat target lesion revascularization by percutaneous or surgical methods

Revision 4.0

4. Composite of cardiac death and myocardial infarction
5. Target vessel failure (TVF)
 - Defined as cardiac death, target vessel myocardial infarction or clinically-driven target vessel revascularization
 - Target vessel failure will be reported when ANY of the following events occur:
 - Recurrent MI occurs in territory not clearly attributed to a vessel other than the target vessel
 - Cardiac death not clearly due to a non-target vessel endpoint
 - Target vessel revascularization is determined
6. Target lesion failure (TLF)
 - Defined as cardiac death, target vessel myocardial infarction (Q wave and non-Q wave), or clinically driven target lesion revascularization (TLR) by percutaneous or surgical methods.
7. All revascularizations (TLR, TVR and non-TVR)
8. Stent thrombosis (definite/probable)
9. Stroke
10. Bleeding per BARC criteria
 - BARC 3 to 5
 - BARC 2 to 5
 - All BARC

4. Investigation Plan

A total of 700 subjects will be enrolled in the United States, and 100 subjects may additionally be enrolled in Japan. Subjects will be enrolled in up to 70 centers over an approximate 10-month period or until study enrollment is completed. A maximum of 140 subjects (approximately 20% of the primary analysis population) may be enrolled at one study center. While all sites are expected to contribute to enrollment, there is no set minimum requirement for the number of subjects enrolled at each study center; however, it is expected that a minimum of five (5) subjects will be enrolled per study center.

Subjects may receive treatment of one or more lesions. Planned staged procedures within 30 days of the index procedure are allowed. Subjects who are enrolled with an attempted implant procedure will be considered part of the intent-to-Treat (ITT) population. ITT subjects implanted with Resolute Onyx stent will be followed through two years. Clinic visit health status assessments will be documented at the 1-month time point. Subject contact health status assessments will be documented at 2 months, 6 months, 1 year, and 2 years. The study will be conducted to allow data collection and analysis for 2 years from treatment of the final subject or until the study has been formally terminated. The total study duration is estimated to be 34 months from first enrolled subject through final follow-up.

5. Sample Size and Power Considerations

5.1. Sample Size for Primary Objective

Based on historical short DAPT studies with high-bleeding risk patient populations (LEADERS FREE, ZEUS, and SENIOR)^{1,2,3,4,5} the weighted average of cardiac death and myocardial infarction at one year was 9.6%. As disproportionately higher rates of STEMI, unstable angina, and multi-vessel disease were identified in the ZEUS study population which could have led to a higher rate of cardiac death, the ZEUS rate was revised. Similarly, the SENIOR rate contribution was derived from the published rates based on subjects with planned one-month DAPT use.

Approximately 3% of CD/MI events occurred in LEADERS FREE study at 30 days. To account for a “one-month clear” population, the weighted CD/MI rate at 12 months will be discounted by 3%, resulting in an average rate of 6.6%. In addition, to account for the 3% population that will also be removed from the denominator of the rates, the expected CD/MI rate between 30 days and one year is more accurately represented as 6.8%.

The performance goal (9.7%) incorporated a clinically acceptable margin of 2.9% to the expected rate.

In defining a “one-month clear” population, an attrition rate of 20% will be applied to account subjects who interrupted or discontinued DAPT (greater than 3 cumulative days) within the first one month of procedure, who were excluded due to events that would prohibit them from discontinuing DAPT beyond one month, who failed to transition from DAPT to single antiplatelet therapy (SAPT) one month after procedure, and who were lost to follow-up. Peri-procedural MIs will not exclude the patient from being considered as “one month clear”. For the secondary endpoints like TLF, all available biomarkers (including peri-procedural) will be forwarded to the CEC to be used towards the adjudication of events.

Assuming a one-sided alpha level of 0.025 and a true event rate of 6.8%, an effective sample size of 1360 subjects will yield a greater than 97% power to reject the null hypothesis. Assuming a 20% attrition rate, a total sample size of 1700 subjects will be needed.

The outcomes from 700 US subjects enrolled in this study will be combined with those of 1000 subjects from the Resolute Onyx arm of the Onyx ONE Study to form the total sample size of 1700. In addition, subjects enrolled in Japan in this study who have completed their one-year follow-up at the time when the 700 US subjects have completed their one-year follow up will also be included in the primary analysis.

6. Statistical Methods

6.1. Analysis Populations

Per the CIP, subjects will be considered enrolled into the trial after the following criteria have been met:

1. The signed and dated informed consent has been obtained
2. The patient and target vessel(s)/lesion(s) have met all of the inclusion and none of the exclusion criteria

Revision 4.0

3. The study stent is introduced into the guide catheter

Intent-to-Treat (ITT): All enrolled subjects. Time zero begins at the date of the index procedure.

As Treated (AT): All ITT subjects who received the Resolute ONYX stent only. Time zero begins at the date of the index procedure.

One-month Clear: All subjects who meet all of the following criteria:

- [REDACTED]
- [REDACTED]
- [REDACTED]

[REDACTED]

[REDACTED]

Event-free is defined as that a subject must not have myocardial infarction (MI) (excluding peri-procedural MIs), repeat coronary revascularization, stroke, stent thrombosis (ARC definite/probable), and death. [REDACTED]

[REDACTED]

As Treated and Intent-to-Treat for one-month clear are:

- As Treated Set for One-month Clear: All AT subjects who are in the one-month clear population. This is the primary cohort for the primary endpoint analysis.
- Intent-to-Treat Set for One-month Clear: All ITT subjects who are in the one-month clear population.

6.2. Description of Baseline Variables

All clinically relevant baseline variables will be tabulated and reported. Categorical variables will be reported using counts and percentages, and continuous variables will be reported by giving the number of known values, the means, medians, standard deviations, interquartile ranges, minimum and maximum values. Baseline demographic and clinical variables will be summarized for the AT, AT one-month clear set.

Revision 4.0

6.3. Kaplan-Meier Analyses

For safety related endpoints, a Kaplan-Meier analysis of event rates at 1 month, 2 months, 6 months, 1 year, and 2 years will also be provided.

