6.4.1. Hypothesis

The primary endpoint of the study will be compared to a pre-specified PG of 9.7%. The study hypotheses are:

$$H_0: \pi \geq 9.7\%$$

$$H_A: \pi < 9.7\%$$

where π denotes the binary rate of cardiac death and myocardial infarction at one year in a one-month clear population [timeframe: one month to one year]. This one-sided test will be carried out at the 0.025 significance level using the binomial exact test.

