6.4.2. Primary Endpoint Definition

The primary endpoint is the binary rate of the composite event rate of cardiac death, and myocardial infarction at one-year post-procedure in a one-month clear population. The numerator will be the number of one-month clear subjects who have cardiac death or myocardial infarction, on or before one-year post-procedure (365 days). The denominator will be the number of one-month clear subjects who either have CEC events on or before one year, or have latest date of all follow-up visits, assessments, or events on or after the lower window of one year follow up.

In addition, the KM event rates at 1 month, 2 months, 6 months, 1 year, and 2 years, as well as the KM plot will be provided.

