6.5.1. Data Collection and Analysis Methods

The data on the CEC adjudication form will be used in the analysis. For secondary endpoints, event rates/success rates, and 95% two-sided confidence interval will be provided. The time-sensitive nature of any response variable will be displayed by using a Kaplan-Meier plot.

The primary analysis for secondary endpoints at follow-up time points (2, 6 months, 1 and 2 years) will be performed for AT one-month clear population, except that the acute success. The secondary analysis for secondary endpoints (except acute success) at all follow-up time points (1, 2, 6 months, 1 and 2 years) will be performed based on the AT set.

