6.7. Analysis for Publications for Extension of Onyx One Global RCT Study

This section describes the planned analyses for publication purpose only. Baseline demographic and clinical data from the pooled Resolute Onyx subjects will be compared to the data from the BioFreedom arm of Onyx One study for ITT, AT, and AT one-month clear sets. The cumulative analysis (from one month to 365 days post procedure) will be performed for the AT one-month clear population and the landmark analysis will be performed for ITT and AT sets on all clinical endpoints and for all subgroups defined in Section 6.6 except the US vs Japan subgroup, Medication Adherent subgroup, and SAPT type after one-month subgroup. The analysis populations for the cumulative and landmark analyses are specified in Tables 1 to 2.

Landmark analyses at 30 days for all clinical endpoints will be performed for the AT and ITT set, and will be compared to the corresponding populations in the BioFreedom arm of Onyx One Global RCT study. The Kaplan Meier method will be used to calculate event rates for events that occur between 31- and 365-days post index procedure. Subjects who died or withdrew before 30 days will be excluded from this analysis. Subjects who experienced non-terminal events (e.g., MI) before 30 days will be included from this analysis. The cumulative incidence function in the presence of a competing risk will be estimated, and comparisons between Onyx and BioFreedom arms will be made using Gray’s test.

Table 1. Analysis Populations for Pooled Cumulative Analysis

Cumulative Analysis	Planned Analysis	Analysis Population for Cumulative Analysis
All clinical endpoints, from one month to one year	Principal effective and safety table	AT one month clear

Revision 4.0

Subgroup analysis from one month to one year	Principal effective and safety table	AT one month clear
--	--------------------------------------	--------------------

Table 2. Analysis Populations for Pooled Landmark Analysis

Landmark Analysis	Planned Analysis	Analysis Population for Landmark Analysis
All clinical endpoints, from 30 days to one year	Principal effective and safety table	ITT/AT
Subgroup analysis from 30 days to one year	Principal effective and safety table	ITT/AT

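### The supplementary Kaplan-Meier rates modestly overstate cumulative incidence for endpoints that leave out some deaths, and SAP 6.7 does not say which rate is shown with Gray's p-value

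*SAP*

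**What the plan says.** **Primary analysis.** The primary endpoint is a binary CD/MI rate from one month to one year (SAP 6.4.2). SAP 6.4.1 adds: "This one-sided test will be carried out at the 0.025 significance level using the binomial exact test". The denominator keeps one-month-clear subjects who have a CEC event by one year or whose last contact falls on or after the lower edge of the one-year window.

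**Supplementary Kaplan-Meier output.**
- SAP 6.3: "For safety related endpoints, a Kaplan-Meier analysis of event rates at 1 month, 2 months, 6 months, 1 year, and 2 years". The sentence goes on to make clear that these are extra to other rates. The SAP does not list which endpoints are safety related.
- SAP 6.4.2, for the primary endpoint: "In addition, the KM event rates at 1 month, 2 months, 6 months, 1 year, and 2 years", with a plot.
- SAP 6.5.1, for secondary endpoints: rates with 95% confidence intervals, and "The time-sensitive nature of any response variable will be displayed by using a Kaplan-Meier plot". Here Kaplan-Meier is named only for the plot.

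**Censoring.** The one written rule, in protocol 12.10, concerns dropouts. Outside SAP 6.7 neither document says what happens to a subject who dies of a cause outside the endpoint.

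**Publication analyses.** SAP 6.7 says of the ITT and AT landmark analysis: "The Kaplan Meier method will be used to calculate event rates for events that occur between 31- and 365-days post index procedure". It then says "The cumulative incidence function in the presence of a competing risk will be estimated" and names Gray's test for Onyx against BioFreedom.

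**The concern.** One minus Kaplan-Meier, with other deaths censored, treats a subject who has died of something else as still at risk of the event. It estimates risk in a hypothetical setting without those deaths. Cumulative incidence gives the share of patients who actually have the event.

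The distinction can matter here. The inclusion criteria (protocol 7.3) select on age 75 or over, active cancer, renal failure, severe liver disease and anemia. For CD/MI, TLF and TVF the competitor is non-cardiac death. For stent thrombosis, stroke, bleeding and revascularization, any death not counted in the endpoint competes. MACE and all-cause death contain every death and have no such problem.

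In SAP 6.7 the stake is agreement between rate and p-value. Gray's test compares cumulative incidences, which depend on mortality outside the endpoint. The Kaplan-Meier rate is built to ignore that mortality. The Onyx side pools a randomised arm with a separate single-arm US and Japan study, so randomisation does not guarantee equal competing mortality against BioFreedom. A table could then pair a Kaplan-Meier difference with a p-value for a different quantity.

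**Working it through.** **1. The plan's own figure.** For n = 1360, goal 9.7%, true rate 6.8% and one-sided alpha 0.025, the exact binomial test succeeds at 110 events or fewer (8.09%). Its exact size is 0.0227 and its power 97.14%, which matches the stated figure of above 97%. The 6.8% is (9.6 − 3)/0.97 = 6.80, and 1360/0.80 = 1700. No step uses Kaplan-Meier, so nothing below changes the sample size, the power or the primary test.

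**2. Inputs for the bias.**
- Event rate over months 1-12: 6.8% (SAP 5.1), taken as the Kaplan-Meier value.
- Two-year rate: 13%, illustrative and not in the documents.
- Competing mortality: 2-8% a year, an assumption. For scale only, protocol 3.1 cites 3.9% one-year all-cause death in an all-comer registry, and 4.2% one-year cardiac death in the drug-coated arm of a high-bleeding-risk trial. The first includes cardiac death. The second is part of CD/MI, TLF and TVF, so it competes only for endpoints that leave cardiac death out.

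**3. Formulas** (constant hazards; t in years; m = annual competing mortality):
- event hazard h1 = −ln(1 − KM)/t
- competing hazard h2 = −ln(1 − m)
- cumulative incidence CIF = h1/(h1 + h2) × [1 − exp(−(h1 + h2)t)]

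**4. Results.** For months 1-12, t = 335/365 = 0.918 and h1 = 0.0767. For two years, t = 2 and h1 = 0.0696.

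| m per year | h2 | CIF when KM = 6.8% | Excess (points) | CIF when KM = 13% | Excess (points) |
|---|---|---|---|---|---|
| 2% | 0.0202 | 6.74% | 0.06 | 12.75% | 0.25 |
| 4% | 0.0408 | 6.68% | 0.12 | 12.50% | 0.50 |
| 6% | 0.0619 | 6.61% | 0.19 | 12.25% | 0.75 |
| 8% | 0.0834 | 6.55% | 0.25 | 12.00% | 1.00 |

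**5. Cross-check from the other direction.** Fix the one-year CIF at F1 = 6.8% and competing death at F2, so KM = 1 − exp[ln(1 − F1 − F2) × F1/(F1 + F2)]. This gives 6.87% at F2 = 2%, 6.94% at 3.9%, 7.02% at 6% and 7.17% at 10%. A simulation of 400,000 subjects with targets of 6.8% and 3.9% gave KM 6.98%, Aalen-Johansen 6.84% and crude proportion 6.84%. With complete follow-up the crude rate and the cumulative incidence agree, and only Kaplan-Meier is high.

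**6. Scale.** At n = 1360 and 6.8%, the 95% half-width is 1.96 × √(0.068 × 0.932/1360) = 1.34 points. The largest months 1-12 excess above is 0.25/1.34, about a fifth of that.

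**7. Kaplan-Meier against the binary rate when subjects are lost.** The binary denominator drops event-free subjects last seen before the one-year window opens at day 335. Kaplan-Meier keeps their partial follow-up. Take KM = 6.80%, m = 2% and a constant loss hazard of 0.0328 a year up to day 335, which removes 2.6% from the denominator. Observed events are then 6.64% of the cohort, and the binary rate is 6.64/0.974 = 6.82%, slightly above Kaplan-Meier. With m = 4% and 4.35% removed it is 6.51/0.9565 = 6.81%. The order of the two rates is therefore not fixed.

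**The case against.** The strongest reply is that this output is secondary. The Kaplan-Meier rates in SAP 6.3 and 6.4.2 are additions, SAP 6.5.1 plans only a plot, and the rates with confidence intervals are not described as Kaplan-Meier. Censoring of other deaths is software default, not a written rule. Protocol 7.4 excludes life expectancy under two years, and the one-month-clear set removes first-month deaths, so competing mortality may be lower than the inclusion criteria suggest. The bias runs against the device: competing death would have to reach about 52% before a true 6.8% appeared as 9.7%. SAP 6.7 already plans the cumulative incidence function. All of this stands, and it sets the priority. It does not settle how non-endpoint death is treated in 6.3, 6.4.2 and 6.5.1, or which estimate accompanies Gray's p-value.

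A reader might infer three stronger things that the documents do not support:
- *All reported one- and two-year rates are biased upward.* The primary rate is binary, and the secondary rates in SAP 6.5.1 are not said to be Kaplan-Meier. Protocol 8.11 places revascularization under effectiveness, so SAP 6.3 may not cover it.
- *The Kaplan-Meier one-year rate must exceed the binary rate.* Step 7 shows that losses can reverse the order.
- *SAP 6.7 lacks a competing-risk method.* It names one. The gap is in the pairing of rate and test, and the Kaplan-Meier sentence concerns only the ITT and AT landmark analysis.

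**Conclusion.** The point holds as a low-priority correction. Under default censoring, the supplementary Kaplan-Meier figures overstate cumulative incidence for CD/MI, TLF, TVF, stent thrombosis, stroke and bleeding where those rates or plots are produced, and for revascularization wherever Kaplan-Meier is used. The size depends on constant hazards and an assumed 2-8% annual competing mortality: about 1-4% in relative terms over months 1-12 (0.06/6.74 to 0.25/6.55) and about 2-8% at two years (0.25/12.75 to 1.00/12.00). The primary conclusion is not at risk. SAP 6.7 leaves open which rate is shown with the p-value, and that holds whatever the mortality turns out to be.

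**What to change.** - **SAP 6.3, 6.4.2 and 6.5.1:** state how death outside the endpoint is handled. For endpoints that do not include all deaths, report Aalen-Johansen cumulative incidence with 95% confidence intervals and the matching plot. The competing event is non-cardiac death for CD/MI, TLF and TVF, and any death not counted in the endpoint for MI alone, stent thrombosis, stroke, bleeding and revascularization. Keep Kaplan-Meier for all-cause death and MACE, and keep censoring for withdrawal and loss.
- **SAP 6.7:** drop the Kaplan-Meier landmark rates for those same endpoints and show the already planned cumulative incidence beside Gray's p-value.

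The cost is a few lines of SAP text and a different option in standard survival software. The rates become slightly less comparable with older publications that used Kaplan-Meier. The primary test, power and sample size do not change.
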